8.3 POPULATIONS FOR ANALYSES

Male and female, aged 18 and above, with a diagnosis of fecal incontinence. For the main and the sub-study, the analyses will follow the intent to treat (ITT) paradigm with all subjects randomized included in the analyses. Subjects with missing values for a particular endpoint will have their missing values imputed using the corresponding overall mean value from all subjects with non-missing data for that endpoint. An adjustment in the ANCOVA error degrees of freedom (subtracting one for each imputed value) will be made to account for the imputation. A similar adjustment for the Wilcoxon rank sum test (adjusting the degrees of freedom for the t-approximation) will also be examined. Similar analyses will be performed for the completer cohorts, i.e., all subjects who completed the 4 week treatment bowel diary and the [REDACTED] sub-study. For the bowel diary study, the modified ITT (mITT) cohort, which comprises those subjects who entered treatment and completed at least 1 week of device use will also be considered.

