6.7 PARTICIPANT DISCONTINUATION/WITHDRAWAL FROM THE STUDY

If signs of a major side effect (e.g., rectal perforation) should occur, the subject will be treated as clinically indicated and Principal Investigator and Sponsor will be notified immediately. Such events will be reported on the case report form.

Patients with AEs will be evaluated by the investigator. An anoscopy will be performed to determine the etiology of anal pain or bleeding and if a significant anal-rectal abnormality is identified the patient will exit the study. Any data collected from a patient who is withdrawn because of an AE will be included in the ITT safety but not effectiveness summary. Any patient with a mucosal abnormality should be followed to resolution. After the treatment period, all individuals who withdraw for reasons other than personal preference (i.e., for medical reasons) and a minimum of 50% of all patients shall undergo an evaluation by anoscopy following the treatment period to assess for device related trauma.

Subjects will be informed that they have the right to withdraw from the study at any time for any reason, without prejudice to their medical care, penalty or loss of benefits. If the subject withdraws, they should be treated with standard of care. The Investigator also has the right to withdraw subjects from the study for any of the following reasons:

- Adverse events which, in the judgment of the Investigator, justify treatment study withdrawal
- Non-adherence to study device use regimen or protocol requirements
- Non-compliance with instructions
- General or specific changes in the subject's condition unacceptable for further treatment in the judgment of the Investigator
- Subject requires use of an unacceptable concomitant medication
- Subject no longer meets the protocol criteria (Section 4.2)
- Subject request
- Administrative reasons

If a subject is withdrawn or discontinued from the study, the primary reason for withdrawal from the study is to be recorded in the source documents and the Case Report Form. All subjects withdrawn prior to completing the study should be encouraged to complete study safety assessments.

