8.2 SAMPLE SIZE DETERMINATION

The sample size determination was based on literature review. In a controlled clinical trial with clonidine, the mean and standard deviation (SD) for weekly FI episodes over a 4 week baseline period was 2.642 and 1.066 respectively in the placebo group.²⁹

Assuming a mean frequency of 2.6 and a very conservative estimated SD of differences (post-pre treatment) of 1.3, a sample size of 13 subjects provides 90% power with a two sided paired t test and an alpha level of 0.05 to detect a 50% reduction (i.e., from 2.6 to 1.3 episodes/week) in the number of episodes of FI. Hence, a sample size of 30 FI subjects per group (i.e., 10mm and separately 13 mm inserts) is more than sufficient.

In order to test whether the treatment provides an improvement up to 60% response rate (50% response) from an assumed historical rate of 30%, the exact one-sample binomial test (2-sided) will be used at the 0.05 level. A sample size of n=30 provides 90% power to detect this effect.

No previous studies have evaluated [REDACTED]. We estimated that FI subjects [REDACTED] will [REDACTED] of the [REDACTED] (i.e., [REDACTED]). If [REDACTED] with a sample size of [REDACTED] in the [REDACTED] and [REDACTED] in the [REDACTED] (i.e., [REDACTED] devices), provides [REDACTED] [REDACTED].

For anoscopy, the sample size of 31 patients (i.e., 52%), provides 80% power to detect an event rate of 5% and 96% power to detect an event rate of 10%. In this context, an event refers to a side effect such as an anal fissure.

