
from 4 week baseline period through 4 week treatment period (approximately 9-12 weeks).] 70% of subjects would have greater than or equal to 50% reduction in incontinence frequency.
 
2.
 
 ▪ Safety (AEs and SAEs) 	
 • The proportion of subjects in whom, during the treatment period, the device will reduce the number of days with FI by 50% as compared to baseline. • The proportion of subjects in whom the device will reduce the volume of FI during the treatment period as compared to baseline. • The proportion of subjects in whom the Minnesota Medical Technologies Anal Insert Device reduces the proportion of FI episodes which are associated with diarrhea. • The proportion of subjects in whom the Minnesota Medical Technologies Anal Insert Device reduces the number of episodes of passive and of urge FI • The proportion of subjects in whom the Minnesota Medical Technologies Anal Insert Device improves the Quality of Life (QOL) related to FI during the treatment period as compared to baseline. • The proportion of subjects in whom the Minnesota Medical Technologies Anal Insert Device will affect the composition of stool leakage during the treatment period as compared to baseline. • The proportion of subjects are satisfied with the Minnesota Medical Technologies Anal Insert Device. • The time for which a bowel movement can be deferred after the occurrence of urgency will be affected by the Minnesota Medical Technologies Anal Insert Device. • The proportion of complete bowel movements will be affected by the Minnesota Medical Technologies Anal Insert Device during the treatment period as compared to baseline. • Treatment with the Minnesota Medical Technologies Anal Insert Device will affect anxiety and depression during the treatment period as compared to baseline. • The Minnesota Medical Technologies Anal Insert Device reduces the use of medications for FI during the treatment period as compared to baseline. 	

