8.4.2 ANALYSIS OF THE PRIMARY AND SECONDARY EFFICACY ENDPOINT(S)

[REDACTED]
detailed methods for the analyses outlined below,

All bowel diary parameters (e.g., stool frequency, form, urgency, use of rescue medications, and FI) will be averaged first for each day and then over 4 weeks (baseline period and the last 4 of 12 weeks (approximately Weeks 9-12, treatment period) in each subject. These responses will also be assessed using ANCOVA models, with the corresponding baseline value as the primary covariate. [During the fitting period (approximately weeks 5-8), bowel diaries and questionnaires will be maintained to determine the right size of device. However, these data will not be used to evaluate the efficacy of the device.]

The analyses of the primary and secondary quantitative endpoints will utilize analysis of covariance (ANCOVA) models using corresponding baseline measurements, if available, as covariates. The adequate relief endpoint will first be summed over 4 treatment weeks, and then assessed using the Wilcoxon rank sum test. Treatment effects between groups (i.e., 10 mm vs 13 mm) will be evaluated, as appropriate with ANCOVA adjusted for the baseline variable. Individual adverse events (AEs) will be summarized and, where appropriate, (i.e., for parameters that are recorded during baseline and treatment bowel diaries such as pain during defecation), the overall frequency of AEs be compared using the Wilcoxon rank sum test. For the volume of FI episodes, a weighted score will be computed as follows (proportion of minor episodes*2 + proportion of major episodes*3).²⁵ An FI episode is defined as any episode of stool leakage that is more than a stain. A “minor FI episode” is more than a stain but not an entire bowel movement. A “major FI episode” is an entire bowel movement.

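### Filling missing outcomes with the observed mean reports the observed-case result as ITT, with a standard error that is too small and no usable rule for missing responders

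*Combined protocol and SAP*

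**What the plan says.** All references are to the combined protocol and SAP.

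- **Missing values (8.3).** For each endpoint, subjects without a value "will have their missing values imputed using the corresponding overall mean value from all subjects with non-missing data". Then: "An adjustment in the ANCOVA error degrees of freedom (subtracting one for each imputed value) will be made to account for the imputation". A similar change for the Wilcoxon test is to be examined. No correction is given for a paired t test or an exact binomial test.
- **Analysis sets (8.3).** ITT is defined by randomization, although the main study has one group and randomizes no one (6.3). Similar analyses follow for completers and for a modified ITT set, "which comprises those subjects who entered treatment and completed at least 1 week of device use".
- **Adverse-event withdrawals (6.7).** "Any data collected from a patient who is withdrawn because of an AE will be included in the ITT safety but not effectiveness summary".
- **Responder test and target.** For a response rate against a historical 30%, "the exact one-sample binomial test (2-sided) will be used at the 0.05 level" (8.2). The primary outcome carries the target that "70% of subjects would have greater than or equal to 50% reduction in incontinence frequency" (8.4.1).
- **Diary data (8.4.2).** Diary parameters "will be averaged first for each day and then over 4 weeks". On the fitting-period diaries: "However, these data will not be used to evaluate the efficacy of the device".

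**The concern.** In a single-arm study the size of the effect and its interval are the result. Filling gaps with the mean of those who stayed adds no information, yet counts the filled subjects as if they had been measured. Precision is therefore overstated even when data are missing completely at random.

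If subjects leave because of discomfort or lack of effect, the ITT analysis gives them the average benefit. The completer and modified ITT sets omit early leavers too. No analysis visible in the plan shows the result if the missing subjects did badly.

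For a yes/no endpoint the rule does not produce a yes or a no. A choice of handling made after the data are seen could move the reported response rate across the 70% target.

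**Working it through.** **Inputs.** n = 60 (4.1, 8.1); mean change 1.3 episodes/week, SD of differences 1.3, null response rate 30% (8.2); responder target 70% (8.4.1). The number missing, k, is assumed, because the plan states none. Here k counts subjects with no usable treatment-period value, not all dropouts.

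**The plan's own figures.** The paired t test with 13 subjects has power 0.911 (0.883 with 12). The exact test with n = 30 and a cutoff of 15 has power 0.903. Both stated 90% figures reproduce and are not at issue.

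**Standard error.** Let k of 60 be filled with the observed mean.

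1. The mean of all 60 equals the observed mean.
2. Filled values add nothing to the sum of squares SS. With the correction, s² = SS/(60 − 1 − k), which is the observed-case variance.
3. The rule's SE is s/sqrt(60). The observed-case SE is s/sqrt(60 − k). The ratio is sqrt((60 − k)/60).
4. True alpha = 2·P(t > t_crit × ratio), on 59 − k df. Half-widths below use SD 1.3.

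| k | SE ratio | SE too small by | True alpha | 95% half-width, rule | Half-width, observed cases |
|---|---|---|---|---|---|
| 1 | 0.992 | 0.8% | 5.2% | 0.336 | 0.339 |
| 2 | 0.983 | 1.7% | 5.4% | 0.336 | 0.342 |
| 3 | 0.975 | 2.5% | 5.6% | 0.336 | 0.345 |
| 8 | 0.931 | 7% | 6.7% | 0.337 | 0.362 |
| 12 | 0.894 | 11% | 7.8% | 0.338 | 0.377 |
| 18 | 0.837 | 16% | 9.9% | 0.339 | 0.405 |

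The formula is exact for a one-sample mean. A simulated ANCOVA (baseline correlation 0.5 and data missing completely at random, both assumed) gave 95% interval coverage of 93.4%, 92.1% and 90.4% for k = 8, 12 and 18. Observed-case ANCOVA gave about 95%.

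**Responders.** Read directly, the rule gives each missing subject the observed proportion.

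- k = 12, 34/48 observed: the filled total is 34 + 12 × 34/48 = 42.5 of 60, or 71%. This is not a whole count, so the exact test has no input. Missing as failures: 34/60 = 57%.
- k = 3, 40/57 observed: 70%. Missing as failures: 40/60 = 67%.

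**Mean reduction.** If the missing subjects had no reduction, an observed 50% becomes 50 × 57/60 = 47.5% with 3 missing and 50 × 48/60 = 40% with 12.

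**Does the test result change?** At the planned effect, t = sqrt(60) = 7.7 under the rule. The observed-case t is 7.2, 6.9 or 6.5 for k = 8, 12 or 18. Against 30%, the exact two-sided test with missing as failures still rejects: 36/60 and 34/60 give p < 0.0001, and 29/60 gives p = 0.003. The conclusion differs only for 23–25 of 52 observed (44–48%; for example 24/52 p = 0.015 against 24/60 p = 0.093) or 21–25 of 48 (44–52%).

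**The case against.** **Missingness may be slight.** Sections 4.1, 5, 8.1 and 8.4.1 together place the 60 as treatment-period entrants. They have retained the device at screening, passed a diary-compliance check and had a fitting period. Diaries are mailed weekly. If available days are averaged, one returned week yields a value. This stands: 1 to 3 missing is plausible, and the error is then small. The 12.5% to 68% quoted in 2.1 is dropout for other anal plugs, so 8, 12 and 18 are illustrations. The count could rise if adverse-event withdrawals' data were removed under 6.7 and then filled under 8.3.

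**The completer analysis gives a sounder interval.** It is not imputed on the treatment diary and divides by its own number. That partly covers precision, but it is no test of poor outcomes among leavers.

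**Stronger readings that a reader might infer:**

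- *Subjects who stop during fitting are given the mean.* The randomization wording in 8.3 leaves room for this, but the sections that place the 60 at treatment entry point the other way.
- *The rule inflates the response rate above the observed one.* If percent reduction were filled and then cut at 50%, every missing subject would become a responder whenever the observed mean reduction is at least 50%: 46/60 = 77% in the 34/48 example. But 8.3 fills the mean of the endpoint concerned, so the direct reading is the observed proportion.
- *The plan has no other rule.* Section 8.4.2 opens with blacked-out text that refers to detailed methods. Only the visible plan can be judged.

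**Conclusion.** The rule is wrong as written and should be fixed before analysis. It labels the observed-case estimate as ITT and understates its standard error by sqrt(observed/60). It gives the exact test no usable value for a missing responder. Sections 6.7 and 8.3 also disagree on whether adverse-event withdrawals count for effectiveness.

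The size depends on a missing count that the plan does not state, from negligible at 1 to 3 missing to an alpha near 10% at 18. The alpha figures assume data missing completely at random. The response-rate gap is 3 points with 3 missing and 14 points with 12. Counting missing as failures is a conservative convention, not the truth.

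A reader might infer that the trial's conclusion is at risk. The figures do not support that: at the planned effect the null is rejected under every handling tried. The differing results need observed rates of about 44–52%, below the 60% and 70% planning values. The harm is to the reported size and precision.

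**What to change.** 1. Delete the mean-imputation and degrees-of-freedom rule from 8.3.
2. In the ITT responder analysis, count subjects with no usable treatment-period diary data as non-responders.
3. For quantitative diary endpoints, state that available treatment-period days are used as a rate. For subjects with none, and for missing questionnaires, use multiple imputation or a likelihood-based model, so that the standard error is valid.
4. That repairs the standard error but not the optimism, so add one sensitivity analysis giving missing subjects zero reduction.
5. Define ITT as treatment-period entrants, in line with 4.1, 5, 8.1 and 8.4.1, and report subjects who stop during fitting separately.
6. Reconcile 6.7 with 8.3 so that adverse-event withdrawals stay in the effectiveness denominator.
7. Keep the completer and modified ITT analyses as supportive. Align all of this with any rule in the blacked-out opening of 8.4.2.

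The cost is wording in 8.3 and 8.4.2 and a sentence in 6.7, with no new data. The downside is a somewhat lower reported response rate, wider intervals and an imputation model to state.

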8.4 STATISTICAL ANALYSES

8.4.1 GENERAL APPROACH

Male and female subjects aged 18 and above, with a diagnosis of fecal incontinence will be consented and screened for inclusion/exclusion criteria. It is anticipated that up to 250 subjects may be screened to result in 60 subjects that qualify via baseline diary data and can retain the device for inclusion in the Treatment Period of the study. Of these, [REDACTED] of the subjects will be recruited for the [REDACTED] sub-study at Mayo Rochester where [REDACTED] performed.

Outcome variables are summarized below.

Primary and secondary outcomes and other variables		
Primary Outcomes	Secondary Outcomes	Mechanism or Moderator Variables
1. Primary Effectiveness Endpoint: A Relative Percentage Change in Episodes of Accidental Bowel Leakage (ABL) Determined by Comparing Treatment Results to Pre-treatment Results From the Baseline Period as Measured by Daily Diary Recordings. [Time Frame: Reduction in accidental bowel leakage	
• A relative percentage change derived by comparing post-treatment Mayo Fecal Incontinence Severity Index (FISS) Scores to pre-treatment (End of Baseline Period) FISS Scores. [Time Frame: FISS score will be calculated at the end of the 4-week baseline period (Weeks 1-4) and the end of the 4-Week Treatment Period (approximately weeks 9-12).] In 50% of subjects, the FISS score will decline by ≥ 3 units.• The proportion of subjects in whom, during the treatment period, the frequency of FI episodes is greater than or equal to 75% lower than the frequency observed during the baseline period.	[REDACTED] [REDACTED]

Protocol Number IRB-18-004642


from 4 week baseline period through 4 week treatment period (approximately 9-12 weeks).] 70% of subjects would have greater than or equal to 50% reduction in incontinence frequency.
 
2.
 
 ▪ Safety (AEs and SAEs) 	
 • The proportion of subjects in whom, during the treatment period, the device will reduce the number of days with FI by 50% as compared to baseline. • The proportion of subjects in whom the device will reduce the volume of FI during the treatment period as compared to baseline. • The proportion of subjects in whom the Minnesota Medical Technologies Anal Insert Device reduces the proportion of FI episodes which are associated with diarrhea. • The proportion of subjects in whom the Minnesota Medical Technologies Anal Insert Device reduces the number of episodes of passive and of urge FI • The proportion of subjects in whom the Minnesota Medical Technologies Anal Insert Device improves the Quality of Life (QOL) related to FI during the treatment period as compared to baseline. • The proportion of subjects in whom the Minnesota Medical Technologies Anal Insert Device will affect the composition of stool leakage during the treatment period as compared to baseline. • The proportion of subjects are satisfied with the Minnesota Medical Technologies Anal Insert Device. • The time for which a bowel movement can be deferred after the occurrence of urgency will be affected by the Minnesota Medical Technologies Anal Insert Device. • The proportion of complete bowel movements will be affected by the Minnesota Medical Technologies Anal Insert Device during the treatment period as compared to baseline. • Treatment with the Minnesota Medical Technologies Anal Insert Device will affect anxiety and depression during the treatment period as compared to baseline. • The Minnesota Medical Technologies Anal Insert Device reduces the use of medications for FI during the treatment period as compared to baseline. 	

Exploratory study
	
 • Evaluate the effects of the Minnesota Medical Technologies Anal Insert Device [REDACTED] • Evaluate if the effects of the Minnesota Medical Technologies Anal Insert Device [REDACTED] • [REDACTED], and the [REDACTED] the Minnesota Medical Technologies Anal Insert Device [REDACTED] • Evaluate [REDACTED] subjects with FI. • Investigate [REDACTED] obtained at baseline. • The Minnesota Medical Technologies Anal Insert Device [REDACTED] • Evaluate [REDACTED] Minnesota Medical Technologies Anal Insert Device [REDACTED] 	
 • [REDACTED] • [REDACTED] • [REDACTED]

8.4.2 ANALYSIS OF THE PRIMARY AND SECONDARY EFFICACY ENDPOINT(S)

[REDACTED]
detailed methods for the analyses outlined below,

All bowel diary parameters (e.g., stool frequency, form, urgency, use of rescue medications, and FI) will be averaged first for each day and then over 4 weeks (baseline period and the last 4 of 12 weeks (approximately Weeks 9-12, treatment period) in each subject. These responses will also be assessed using ANCOVA models, with the corresponding baseline value as the primary covariate. [During the fitting period (approximately weeks 5-8), bowel diaries and questionnaires will be maintained to determine the right size of device. However, these data will not be used to evaluate the efficacy of the device.]

The analyses of the primary and secondary quantitative endpoints will utilize analysis of covariance (ANCOVA) models using corresponding baseline measurements, if available, as covariates. The adequate relief endpoint will first be summed over 4 treatment weeks, and then assessed using the Wilcoxon rank sum test. Treatment effects between groups (i.e., 10 mm vs 13 mm) will be evaluated, as appropriate with ANCOVA adjusted for the baseline variable. Individual adverse events (AEs) will be summarized and, where appropriate, (i.e., for parameters that are recorded during baseline and treatment bowel diaries such as pain during defecation), the overall frequency of AEs be compared using the Wilcoxon rank sum test. For the volume of FI episodes, a weighted score will be computed as follows (proportion of minor episodes*2 + proportion of major episodes*3).²⁵ An FI episode is defined as any episode of stool leakage that is more than a stain. A “minor FI episode” is more than a stain but not an entire bowel movement. A “major FI episode” is an entire bowel movement.

